#### Surgery Patients

Months 1-59:

- Recruitment of patients
- Data Collection

Month 60: Completion of Study

## 6. STUDY PROCEDURES

### 6.1 Subject Identification

#### Healthy Volunteers:

Healthy donor participants will be recruited publicly using two separate procedures:

Procedure 1 - Paper poster advertisements detailing contact information i.e. email and telephone number of the Dermatology Research Team will be placed around local buildings including NHS, University and local office sites. Dermatology Research Team will also use the NHS intranet site to advertise the study. When the volunteers contact the Dermatology Research Team they will be sent

the study information sheet, study consent form and screening questionnaires by email to complete and return. They will also be given the option to complete the details via the online link that will take them through procedure 2. Once returned to the Dermatology Research Team, volunteer will be screened for eligibility. Those eligible will be invited to attend a research clinic appointment.

Procedure 2 – Posters will be distributed in areas of high footfall i.e. Nexus Metro stations. The poster will give brief detail of the volunteers that we are looking to recruit and the contact details will be for Alcyomics Ltd. There will be a QR code for potential volunteers to access further information. The QR code will take the person to a webpage linked to the Alcyomics website. On this page they will find the full detail of the study including the information sheet and study consent form including a link to the Alcyomics privacy policy. After consents are completed, they will be taken to the questionnaire to complete. The details received by Alcyomics will be sent to the Dermatology Research Team for them to book a time for the healthy volunteer to attend a research clinic appointment.

The following will then take place during their research clinic appointment:

The research nurse will confirm participant's identity and eligibility.  
Confirm participant understands the study, and is willing to proceed with their appointment. The participants will have previously consented to the study however they will be asked if there have been any changes to the information given since their original consent and also asked to physically sign consent for the study on this visit. Take the samples by following the study protocol.  
The study protocol and standard operating procedures will be used.

Participants will not be recruited through Patient Identification Centres (PICs)  
Participants will be recruited by publicity, displaying posters and by advertisement on the NHS intranet website

Alcyomics' contact with the volunteer will be to discuss the project to see if they are suitable, and review the screening questionnaire. The sample information received by Alcyomics will be anonymised and there will be no link to trace the identity of the sample donors.

### **Sub-Study – Rheumatoid Arthritis (RA) Patients:**

The process of patient identification and recruitment will differ according to the target group (*RA Sub-study Group [1]* or *RA Sub-study Group [2]* as described).

#### **RA Sub-study Group (1)**

(To assess the safety of peptides for potential use in clinical trial).

To facilitate identification of RA patients known to be of HLADRB0401 or 0404 tissue types due to participation in previous observational research, a departmental database of such individuals who have consented to be approached for future studies may be utilised. Such individuals will be approached during planned hospital visits by a member of their usual care team or the rheumatology research team, and provided with a written information sheet. To facilitate identification of RA patients known, due to participation in previous observational research, to be of HLADRB0401 or 0404 tissue types, or to be autoantibody seropositive (and hence most likely to be HLADRB0401 or 0404 on screening), a departmental database, of those who have consented to be approached for future studies, may be utilised. Such individuals will be approached during planned hospital visits by a member of their usual care team or the rheumatology research team, and provided with a written information sheet. Alternatively, information sheets may be posted to such individuals by a member of the rheumatology or dermatology research team, together with contact information for the research nurse to discuss further. If the patient wishes to join the study, they can inform the research team who will arrange for a screening appointment.

#### **RA Sub-study Group (2)**

(To assess the responses of RA patients to biologics and monitor the response post therapy).

RA patients will be identified the Rheumatology outpatient department. Potentially eligible individuals will be approached by a member of their usual clinical care team and, if interested in participation will be provided with a written information sheet by the same individual or a member of the rheumatology research team. Potentially eligible patients who are retrospectively identified by their clinical team can also be recruited to the study. In this instance, a member of their clinical team may arrange for a participant information sheet to be posted to the patient together with contact information for the rheumatology research team to discuss further. If the patient wishes to join the study, then they can inform the rheumatology research team who will arrange for a screening appointment. The study will also be advertised on posters displayed in rheumatology out-patient departments. Patients who contact the trial team via the poster campaign will be discussed with their primary consultant before being sent trial specific information as above. Finally, patients may be identified by consulting a departmental database; such patients will also be discussed with their primary consultant before being sent trial specific information as above.

### Surgery Patients

Participants will be recruited at a pre-surgery clinic visit. The surgery patients will be given an Information sheet about the study. Participants will be screened by the completion of a Surgery Patient Consent form and Questionnaire.

The surgical team identify the participants and take the blood samples at a predetermined clinic visit and the excess skin samples at the time of surgery by following the study protocol.

The study protocol and standard operating procedures will be used.

Participants will not be recruited through Patient Identification Centres (PICs)

## 6.2 Screening Visit and Consent

Before any study procedures can take place all participants must have provided full written informed consent to participate in the study.

The Chief Investigator is responsible for ensuring that informed consent for study participation is given by each subject. An appropriately trained Doctor or Research Nurse may take consent. If no consent is given a subject cannot be entered into the study.

### Healthy Volunteers:

The consent process for healthy volunteers is as follows:

The potential volunteer will make contact with either the research nurse (procedure 1 above) or Alcyomics via the website link (procedure 2 above) Either method, they will be provided with a study information sheet, study consent form and screening questionnaire. The volunteer reads the information sheet and has at least 24 hours to decide if they want to participate. The participant will complete the screening questionnaire and consent forms and send back to the dermatology team OR they will complete these electronically and they will be sent on to the Dermatology Team.

At the research clinic appointment a research nurse will discuss the completed forms, ensuring that the detail is still correct and making any changes if applicable. The study, the nature of the research and what is involved is discussed with the participant and they have the opportunity to ask any questions. The research nurse ensures the potential volunteer understands the benefits (or lack of benefits), risks and burdens before gaining a second consent The participant is able to make a free choice if they wish to proceed and must be capable of signing the study consent form for themselves.. The consent form will then be countersigned by the research person taking consent The study consent form will be retained in the study investigator site file, a copy will be entered into the patient notes electronic medical record and a copy will be given to the participant.

Healthy volunteers have the option to agree to consent to provide further study samples at the sponsor's request. This is entirely voluntary as stated in the Patient Information Sheet. A maximum of

3 sets of skin punch biopsies (2 biopsies per set) and 3 further 70ml blood samples may be taken after a minimum of 7 days from the previous sample collection date.

### **Sub-Study – Rheumatoid Arthritis (RA) Patients:**

The consent process for RA patients is as follows:

#### **For RA Sub-study Group (1)**

(To assess the safety of peptides for potential use in clinical trial).

All potential participants will have at least 24 hours to consider their willingness to participate in the study, and the opportunity to discuss the study further with a study investigator before signing the consent form. It will be made clear to patients that they are free to withdraw their consent to participate in the study at any time, and that withdrawal from the study will not impact their routine clinical care.

#### **RA Sub-study Group (2)**

(To assess the responses of RA patients to biologics and monitor the response post therapy).

All potential participants will have at least 24 hours to consider their willingness to participate in the study, and the opportunity to discuss the study further with a study investigator before signing the consent form. At each study visit, the patient will be asked to confirm their willingness to continue participation in the study. It will be made clear to patients that they are free to withdraw their consent to participate in the study at any time, and that withdrawal from the study will not impact their routine clinical care.

### **Surgery Patients**

The consent process for surgery patients is as follows:

The research team makes contact with the potential surgery patient volunteer via email or telephone and provides information about the study both verbally and written in the form of the surgery patient information sheet. The surgery patient reads the information sheet and has at least 24 hours to decide if they want to participate. The research team will arrange to go through the surgery patient consent form (REC approved), explaining the study and what is involved in order to understand the purpose and nature of the research. The research team ensures the potential surgery patient understands what the research involves, its benefits (or lack of benefits), risks and burdens, is able to make a free choice and capable of consenting for themselves. The potential surgery patient is given the opportunity to ask question to clarify any aspects of the study. The subject will be asked to sign the consent form which will then be countersigned by the person taking consent and will be retained in the study site file, with a copy placed in the patient notes.

Surgery patients may be asked to return to the study to provide further blood samples. Patients will be given the option to consent to this element of the study using the consent form. This is entirely voluntary as stated in the Surgery Patient Information Sheet.

## **6.3 Withdrawal of Consent**

All patients are able to withdraw consent at any time in the process of the study. In doing this they will no longer be actively participating, but all data collected up to this point may be included in the study analysis unless the patient also withdraws the consent to use the data.

## **6.4 Additional screening procedures**

All consenting individuals will undergo the following procedures at screening:

- Eligibility check. This is to ensure potential participants fulfil the eligibility criteria for one of the target populations to be enrolled in the study (see *Section 5.2*).
- Recording of demographic data including age, gender and race.

- Recording of previous DMARD usage.
- Recording of medical history and concomitant medications.

If not known, blood may be drawn to determine HLA tissue type of RA patients being considered for the RA Sub-study Group (1).

**Note** that the baseline visit may occur simultaneously with the screening visit providing all eligibility criteria are confirmed as being fulfilled at that time. If Screening and Baseline visits are not combined the Baseline visit should take place a maximum of 28 days after the Screening visit.

## **7. STUDY ASSESSMENTS**

### **7.1 Biological Samples**

Healthy volunteers or RA Patients Sub-Study 1 and Surgery Patients will be asked to provide blood samples at baseline and RA Sub Group 2 only to provide blood samples during therapy as indicated in the study flow chart and detailed below.

For Healthy volunteers and RA Patients Sub-Study 2x 4mm skin biopsies will be taken either at the time of the baseline blood sample or + 7 to 14 days after the baseline blood samples depending on the testing protocol. The HV and RA Patients (sub-group 1) will be asked to return to the clinic for removal of the skin biopsy suture one week later. All samples will be collected using standard NHS protocols. Samples and data will be held until such time as they become unusable for study, or until a participant asks for them to be withdrawn from further study, at which point they will be disposed of according to regulations in force at the time.

Skin samples from Surgery Patients will only be obtained as excess skin samples at the time of their surgery.

### **7.2 Baseline Visit.**

Study procedures to be carried out during the baseline visit will differ according to the study population into which the volunteer has been enrolled, as outlined below.

#### **7.2.1 Healthy Volunteers:**

These procedures will be carried out by the Dermatology Research Team in the Dermatology Clinic, RVI.

- 70ml blood sample will be taken at the first clinic visit which will include screening for common viruses and HLA (Human Leucocyte Antigen) genotypes. Blood is used to isolate peripheral blood mononuclear cells (PBMC's) which are used in the assays or further processed to generate monocyte derived dendritic cells (Mo DC). 5mLs of the blood is used for serum collection which is used in the skin assay
- 2 x 4mm Skin biopsy (see Section 7.3). The skin biopsies are dissected and used for the skin assay.

#### **7.2.2 Sub-Study – Rheumatoid Arthritis (RA) Patients:**

##### For RA Sub-study Group (1)

(To assess the safety of peptides for potential use in clinical trial).

- Blood draw for research (60ml). Blood is used to isolate peripheral blood mononuclear cells (PBMC's) which are used in the assays or further processed to generate monocyte derived dendritic cells (Mo DC). 5mLs of the blood is used for serum collection which is used in the skin assay.

##### For RA Sub-study Group (2)

(To assess the responses of RA patients to biologics and monitor the response post therapy). These procedures will be carried out by the Rheumatology Research Team at the Musculoskeletal Unit, Freeman Hospital.

- Patient Global Health questionnaire (visual analogue scale).
- Physician-reported Global Assessment questionnaire (visual analogue scale).
- 28-joint swollen and tender joint count (SJC, TJC).
- Blood test for CRP and ESR (NHS laboratories).
- Blood draw for research (70ml). Blood is used to isolate peripheral blood mononuclear cells (PBMC's) which are used in mixed lymphocyte inhibitor assays using therapeutic antibodies.
- The DAS28-CRP, DAS28-ESR and CDAI scores will be calculated (awaiting results of contemporaneous blood results where needed).

### 7.2.3 Surgery Patients

These procedures will be carried out by the Surgical team at the RVI or Freeman Road Hospital.

- A 70ml blood sample will be taken at a pre-surgery clinic visit.
- Blood draw for research (70ml). Blood is used to isolate peripheral blood mononuclear cells (PBMC's) which are used in the assays or further processed to generate monocyte derived dendritic cells (Mo DC). 5mLs of the blood is used for serum collection which is used in the skin assay

The collected excess skin samples are dissected and used for the skin assay

### 7.3 Skin Biopsy

Skin Biopsies will be performed in line with NuTH routine procedures. Two 4mm punch biopsies will be obtained from either the lower back, buttock or lower abdominal areas depending on volunteer or RA patient preference. The biopsy will be dissected into 10 pieces for the Healthy Volunteer and Group 1 RA study. Healthy volunteer biopsies may also be dissected and skin cells, fibroblasts and keratinocytes isolated and a 3D skin model developed in line with a high throughput assay development.

### 7.4 Follow-up Samples

#### 7.4.1 Healthy Volunteer / RA Patient Sub-Study Group 1

- Samples ( taking of 2x 4mm biopsies or extra 70ml blood sample) will be taken either at the same time as the baseline visit or + 7 to 14 days after baseline as directed according to laboratory requirements and patient availability:

2 x 4mm Skin biopsy (defined as 1 x skin biopsy). The skin biopsies are dissected and used for the skin assay.

Patients enrolled in this group will only require further follow up for the removal of sutures, as indicated in the study flow chart, one week after the biopsy (see *Schedule of Events*, 7.5.1, Table 1).

#### 7.4.2 RA Sub-study Group 2

These patients will be followed prospectively in order (i) to determine treatment response and (ii) to monitor for the development of anti-drug antibodies by the developed *in vitro* test and confirmatory serum anti-drug antibody assays and drug levels. Follow-up visits will take place at weeks 12(+/- 2 weeks), 24

(+/- 2 weeks), 36 (+/- 2 weeks), 48 (+/- 2 weeks), 60 (+/- 2 weeks), and 72 (+/- 2 weeks),. At each of these visits the following procedures will be undertaken (see also *Section 7.5, Table 2*):

- Patient Global Health questionnaire (visual analogue scale).
- Physician-reported Global Assessment questionnaire (visual analogue scale).
- 28-joint swollen and tender joint count (SJC, TJC).
- Blood test for CRP and ESR (NHS laboratories).
- Blood draw for research (20ml). 15ml blood is used to develop the anti-drug antibody assay and 5ml as serum to screen for anti-drug antibodies.
- The DAS28-CRP, DAS28-ESR and CDAI scores will be calculated (awaiting results of contemporaneous blood results where needed)

## 7.5 Schedule of Events

Procedures	Screening Day -90 - Day 0.	Baseline Day 0	Follow-up  Day 7 to14 days after baseline	Follow-up +7 days
Informed consent	x			
Eligibility check	x			
Demographic data	x			
Medical History	x			
Concomitant medication	x			
NHS blood 		X 		
Research blood 	X 	X 		
Skin Biopsy 		x	Or x	
Removal of biopsy Suture			x	Or x

**7.5.1 Healthy Volunteers + Sub-study Group [1]** - To assess the safety of peptides for potential use in clinical trial and use of HV skin and blood sample for development of 3D skin model.

**Table 1. Schedule of Events - HV + RA Sub study Group 1**

Routine NHS bloods (RA patients only); additional blood may be taken for routine purposes.

Total blood draw during the course of the study, including blood for NHS and Research, will not exceed 100mls (and blood draw for clinically indicated NHS testing will be prioritised within this volume if needed).

10mls will be used for HLA typing at screening, collected in an EDTA tube. (Screening – 7 -28 days from baseline for HLA typing if not known to be of eligible HLA tissue type at screening).

70mls blood for research at baseline visit will be drawn into the following tubes: 7x10ml Heparin tubes; screening and baseline visits may be combined IF already known to be of an eligible HLA tissue type at screening.

Two 4mm skin punch biopsies from either the abdomen or buttocks will either be taken at baseline or + 7 to14 days after baseline following the 70mls blood draw- depending on the assay configuration at the time of the patient recruitment and by arrangement with the patient (hence the “Follow-up” visit may be combined with the Baseline visit). This is done with local anaesthetic and will require a small stitch and will leave a small scar after the skin biopsy. The patient will be requested to return to the clinic one week after the biopsy has been taken in order to have the stitch removed.

Procedures	Screening Day -28 - Day 0.	Baseline Day 0	Week 12 +/-14 days	Week 24 +/-14 days	Week 36 +/-14 days	Week 48 +/-14 days	Week 60 +/-14 days	Week 72 +/-14 days
Informed consent	x							
Eligibility check	x							
Demographic data	x							
Medical History	x							
Concomitant medication	x							
Previous DMARD usage	x							
Patient Global Health questionnaire		x	x	x	x	x	x	x
Physician Global Assessment		x	x	x	x	x	x	x
SJC/TJC [28]		x	x	x	x	x	x	x
NHS blood 		x 	x 	x 	x 	x 	x 	x 
Research blood 		x	x	x	x	x	x	x
Disease activity calculations		x	x	x	x	x	x	x

**7.5.2 RA Sub-study Group [2]** - To assess the responses of RA patients to biologics and monitor the response post therapy

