## STUDY SUMMARY

Study Title	Development of an in vitro assay for drug safety and efficacy and skin sensitivity
Internal ref. no. (or short title)	Safety testing of novel compounds and drugs
Study Design	Laboratory
Study Participants	Healthy Volunteers / Rheumatoid Arthritis (RA) Patients /Surgical Patients ( Sub-Studies )
Planned Size of Sample (if applicable)	
Healthy Volunteer          Recruit 4-6 participants per week          1 set of skin punch biopsy (2 biopsies per set) per healthy volunteer          60-70ml blood per healthy volunteer          For patients who have opted in to consent to provide further samples a maximum of 3 sets of skin punch biopsies (2 biopsies per set) and 3 sets of 70 ml of blood.
 
Sub-Study : Rheumatoid Arthritis Patients          Recruit 40-50 per 12 months, 80-100 over 24 months          1 x 60-70ml blood and further maximum 120ml in serial (20ml x 6 blood samples)
 
Sub-study :Surgical Patients          1x 70ml blood at pre-surgical clinic visit          Excess skin sample taken at time of surgery ( minimum 2x 4mm)

Follow up duration (if applicable)	NA
Planned Study Period	5 years
Research Question/Aim(s)	The development and use of in vitro skin assays to predict adverse responses to compounds including drugs and cellular therapies
Funder and financial and non-financial support given	
Alcyomics Ltd - Payment of research staff, research nurses, funding study consumables, vouchers for participants.
 
Vouchers  Healthy Volunteer:
 
 
£50.00 voucher for 1 set of skin biopsies (2 biopsies per set) and 1 set of 70ml blood sample
 
 
For patients who have opted in to consent to provide further samples:
 
 
£25.00 voucher per 70 ml blood sample and £25.00 voucher per 1 set of skin punch biopsy (2 biopsies per set)
 

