	
 
• A maximum of £150.00 for blood and skin punch biopsies samples
 
 
Rheumatoid Arthritis Patients Sub Study 1
 
 
• £50.00 voucher for skin biopsies (x2) and 1x blood sample
 
• £25.00 voucher per blood sample ( )
 
• A maximum of £150.00 for a series of blood samples
 
 
Rheumatoid Arthritis Patients Sub Study 2
 
 
• £25.00 voucher per blood sample
 
• A maximum of £150.00 for a series of blood samples
 
 
Surgery Patients Sub Study 3
 
 
• £25.00 voucher per blood sample
 

Role of study sponsor and funder	Alcyomics Ltd is responsible for the study design, conduct, data analysis and interpretation, manuscript writing, and dissemination of results and controls the final decision regarding any of these aspects of the study.
Key Words:	Safety and efficacy drug testing ; immunotoxicology; adverse immune reactions ; in vitro pre-clinical testing, novel diagnostics

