**Table 2. Schedule of Events RA Sub-Study Group 2**

NHS bloods will include CRP and ESR; additional blood may be taken for routine purposes.

Total blood draw, including blood for NHS and Research, will not exceed 70mls at baseline + 6x20ml (120mls) during therapy (and blood draw for clinically indicated NHS testing will be prioritised within this volume if needed).

70mls blood for research at baseline visit will be drawn into the following tubes: 10ml Heparin tubes x 7; 1x 5ml serum tube

15ml blood for research will be drawn into Heparin tubes and 5 ml into serum tube .

Procedures	Baseline Day 0 pre surgery clinic visit	Time of surgery
Informed consent	x	
Eligibility check	x	
Demographic data	x	
Medical History	x	
Concomitant medication	x	
Research blood 	X 	
Skin Sample		Excess skin only

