### 7.6 Recall of Healthy Volunteers and potentially Surgery Patients

In the case where healthy volunteers (or surgery patients) may be recalled for further testing, this recall is entirely voluntary as stated in the Patient / Surgery Patient Information Sheet. The healthy volunteer /surgery patient will sign a separate line on the Consent Form indicating their agreement. If it is necessary to contact the healthy volunteer/ surgery patient in the future a member of the study team will contact the healthy volunteer/ surgery patient and ask if they are willing to provide further biological samples. To a maximum of 3 skin biopsies (1 Skin biopsy = 2 x 4mm punch biopsies as defined in 7.4.1) and 3 further 70ml blood samples.

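### The 100 ml whole-study blood cap in Table 1 leaves no room for any of the further 70 ml draws allowed to healthy volunteers; the 190 ml Group 2 cap is fully used by research blood

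*Protocol*

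**What the plan says.** **Healthy volunteers.** Table 1 in section 7.5.1 is titled for healthy volunteers and RA Sub-study Group 1. Its footnote 2 reads: "Total blood draw during the course of the study, including blood for NHS and Research, will not exceed 100mls". Section 7.2.1 and footnote 4 of the table set the baseline research draw at 70 ml.

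Three other places provide for more blood from volunteers who opt in:

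- Section 6.2 says that "3 further 70ml blood samples may be taken after a minimum of 7 days from the previous sample collection date".
- Section 7.6, on recall, repeats the allowance: "as defined in 7.4.1) and 3 further 70ml blood samples".
- The Study Summary gives "a maximum of 3 sets of skin punch biopsies (2 biopsies per set) and 3 sets of 70 ml of blood", without saying whether the first set is counted.

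**RA Sub-study Group 2.** Footnote 2 of Table 2 says that NHS and research blood together "will not exceed 70mls at baseline + 6x20ml (120mls) during therapy". It adds that "blood draw for clinically indicated NHS testing will be prioritised within this volume if needed". Sections 7.2.2 and 7.4.2 give the research draw as 70 ml at baseline and 20 ml (15 ml for assay development, 5 ml for serum) at each of six follow-up visits. They list NHS laboratory CRP and ESR at all seven visits.

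**The concern.** A blood cap is a commitment to participants and a rule for site staff. In Table 1 it is written for the whole study and names healthy volunteers, yet the consent and recall sections permit draws that go past it. As written, the first recall sample from an opted-in volunteer exceeds the stated limit, and 100 ml understates what that volunteer may give.

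In Group 2 the cap includes NHS blood but has been set equal to the research blood alone. Keeping to it means giving up part of a research sample at each visit. At follow-up that is the blood for developing the anti-drug antibody assay or the serum for screening, and no text says which gives way.

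**Working it through.** All volumes are the Protocol's own; only addition is needed.

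**Healthy volunteers**

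Inputs: cap 100 ml (Table 1, footnote 2); baseline 70 ml (7.2.1; Table 1, footnote 4); further draws of 70 ml, up to three (6.2, 7.6).

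- Scheduled visits only: 70 ml, within the cap. The cap works for the core schedule.
- Room after baseline: 100 − 70 = 30 ml. Since 30 < 70, no further draw fits.
- Total after k further draws, 70 + 70k: 140 ml (k = 1), 210 ml (k = 2), 280 ml (k = 3).
- If the Summary's three sets include baseline, the maximum is 3 × 70 = 210 ml.
- With the Summary's lower baseline figure of 60 ml, the totals are 130, 200 and 270 ml. All still exceed 100 ml.

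The voucher terms show that the further draws are planned. The Summary pays £25 per 70 ml blood sample and £25 per biopsy set, with "A maximum of £150.00 for blood and skin punch biopsies samples", and 3 × (25 + 25) = 150. That matches three sets but does not settle whether baseline is one of them.

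**RA Sub-study Group 1 (same table).** At most 10 ml for HLA typing plus 70 ml at baseline = 80 ml, leaving 20 ml for NHS blood. The cap holds.

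**RA Sub-study Group 2**

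Inputs: cap 70 + 6 × 20 ml, NHS and research together (Table 2, footnote 2); research 70 ml at baseline (7.2.2) and 15 + 5 = 20 ml at six visits (7.4.2); CRP and ESR at seven visits, volume not given.

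- Cap: 70 + 6 × 20 = 190 ml.
- Research: 70 + 6 × (15 + 5) = 190 ml.
- Left for CRP/ESR: 190 − 190 = 0 ml in total, and 0 ml at each visit (70 − 70; 20 − 20).
- If baseline research blood is 60 ml, as the Summary's 60–70 ml range allows, 70 − 60 = 10 ml is free at baseline and still nothing at the six follow-up visits.

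**The case against.** **The volunteer cap concerns the scheduled visits.** Footnote 2 sits on the research blood row of a table with columns for screening, baseline and two follow-up slots, and none for recall. Recall has its own section, consent line, maximum and 7-day interval. The clause giving NHS testing priority suits RA patients, since footnote 1 confines NHS bloods to them. This is probably what was intended, and it stands as an account of intent. It does not cure the text: the table title names volunteers, the limit runs over the course of the study, and no sentence exempts recall.

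**Group 2 already has a rule.** Staff can take NHS blood first and reduce the research sample. This also stands. A reader might infer that site staff cannot obey the Group 2 text at all; the priority clause shows that they can. What remains is that the 70 ml and 20 ml in sections 7.2.2 and 7.4.2 then become upper limits, reduced at every visit where CRP/ESR blood is taken within the cap.

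**Stronger readings the documents do not support.**

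- That the volumes are unsafe: the Protocol gives no threshold from which this could be argued.
- That volunteers are misinformed: the further draws are stated openly in three places and consented separately, and the information sheet is not among the documents.
- That the Group 2 baseline tubes already exceed the cap: their nominal capacity is 7 × 10 + 5 = 75 ml, but footnote 3 says 70 ml is drawn into them. The surgical list (6 × 10 + 5 = 65 ml for a 70 ml draw) shows that these lists are approximate.
- That the scheduled visits themselves breach Table 1, because section 7.4.1 mentions an extra 70 ml sample. Table 1 shows no research blood at follow-up, so whether that sample adds to baseline is unclear.

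**Conclusion.** The volunteer point holds as a conflict of wording. After baseline, 30 ml remains against 70 ml per further draw, so none fits. The permitted total is 140 ml after one draw and 280 ml after three, with a maximum of 210 ml if three sets includes baseline. This rests only on reading footnote 2 as written.

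The Group 2 point is secondary: a cap that includes NHS blood leaves 0 ml for it once the stated research volumes are drawn. It can be kept by cutting research blood. How large the cut would be cannot be computed, because the Protocol gives neither a CRP/ESR volume nor a minimum assay volume. A reader might infer a loss of assay performance, but nothing in the document shows one.

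Severity is modest. No sample size, endpoint or analysis is affected. The text should still be corrected, because the Protocol's own draws exceed one stated participant limit and use up the other.

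**What to change.** - **Table 1, footnote 2:** state that 100 ml covers the scheduled, non-recall visits only. Add a separate overall maximum for volunteers including recall (280 ml, or 210 ml if three sets includes baseline), with the existing 7-day minimum interval.
- **Study Summary, 6.2 and 7.6:** say in the same words whether the three sets include baseline.
- **Section 7.4.1:** say whether the extra 70 ml sample is a recall draw or adds to baseline, so that the scheduled-visit cap can be checked against it.
- **Table 2, footnote 2:** make the 190 ml cap research-only, or raise it by the local CRP/ESR volume for seven visits.
- **Participant information:** check that it gives the same maxima.

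The cost is a wording amendment with no new procedure. The downside is a higher disclosed maximum blood volume.
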